The CDC guidelines for PrEP indicate that HIV testing is required before PrEP initiation to confirm the person does not have HIV. When oral PrEP is used, it is recommended to repeat HIV testing every 3 months before refilling or reissuing the PrEP prescription. When CAB LA PrEP is used, HIV testing is recommended every 2 months, at the time the injection is administered.⁷ HIV testing for PrEP should consist of a laboratory antigen/antibody test or a point-of-care fingerstick antigen/antibody test; rapid tests using oral fluids lack the sensitivity to detect recent infection.⁷

PrEP clinical care represents an opportunity to provide reproductive & sexual health-related services, such as STI screening. The CDC guidelines for PrEP recommends regular screening for syphilis, gonorrhea and chlamydia.⁷ A systematic review of 91 PrEP programs implementing STI testing services in 32 countries found that only 70% of PrEP programs conducted STI screening before PrEP start, and 70% screened for STI every 3 months. However, in high-income countries, screening was high for gonorrhea (92%), chlamydia (92%) and syphilis (87%), but low for hepatitis A (18%) and hepatitis C (43%).¹² In the US, a survey study found that among 809 current or former PrEP users, 91% reported receiving HIV testing at every PrEP care visit. As for STI screening, a blood sample, urine/urethral swab or a rectal swab was collected at every PrEP care visit in 67%, 57% and 36% of participants, respectively.¹³

It is important to understand patterns of PrEP use among people with incident HIV diagnosis to

improve public health and clinical practice. This study will also provide crucial real-world evidence on incident HIV diagnoses on PrEP, PrEP coverage, HIV testing and STI screening in individuals on either oral or LA PrEP.

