7. RESEARCH METHODS

7.1. Study Design

A cohort study using secondary data from the OPERA[®] (Observational Pharmacology Epidemiology Research & Analysis) cohort will be used to answer the study objectives. OPERA is a multi-site observational database collecting data prospectively from the complete electronic health records (EHR) from clinical care throughout the US.

[figure not shown]
Analyses to meet the study objectives will be conducted twice during the study period. Analysis #1 will include data from 01JAN2021-31DEC2023 (Obj. 1-1a) and from 21DEC2021 to 30JUN2024 (Obj 2-6). Analysis #2 will be a repeat of Analysis #1 with data from 1JAN2021-31DEC2024 (Obj. 1-1a) and from 21DEC2021 to 30JUN2025 (Obj 2-6). A

summary of the study design is provided in Table 1 (exposure groups, index date, censoring criteria, endpoints) and in Figure 1 (timeline).

Table 1. Summary of study design

		Analysis #1	Analysis #2
Obj 1 Among all people without HIV in OPERA	Exposure groups	Calendar years	Calendar years
	Index date	NA	NA
	Censoring criteria	NA	NA
	Endpoints	HIV diagnosis	HIV diagnosis
Obj 1a Among people with a new HIV diagnosis	Exposure groups	PrEP use (never, use within ≤12 months before diagnosis, use >12 months before diagnosis)	PrEP use (never, use within ≤12 months before diagnosis, use >12 months before diagnosis)
	Index date	Date of HIV diagnosis	Date of HIV diagnosis
	Censoring criteria	NA	NA
	Endpoints	NA	NA
Obj 2-5 Among PrEP users	Exposure groups	Oral PrEP, CAB LA PrEP	Oral PrEP, CAB LA PrEP
	Index date	Start of first PrEP regimen during the study period	Start of first PrEP regimen during the study period
	Censoring criteria	Death, loss to follow-up (12 months after last clinical contact), study end (30JUN2024), 12 months after index date	Death, loss to follow-up (12 months after last clinical contact), study end (30JUN2025), 12 months after index date
	Endpoints	HIV diagnosis, PrEP coverage, HIV testing, STI screening, STI diagnoses	HIV diagnosis, PrEP coverage, HIV testing, STI screening, STI diagnoses
Obj 6 Among people who could benefit from PrEP	Exposure groups	NA	NA
	Index date	First OPERA visit with indication for PrEP during study period	First OPERA visit with indication for PrEP during study period
	Censoring criteria	Death, loss to follow-up, study end (30JUN2024), 12 months after index date, PrEP initiation	Death, loss to follow-up, study end (30JUN2025), 12 months after index date, PrEP initiation

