	Endpoints	HIV testing, HIV diagnoses, STI screening, STI diagnoses	HIV testing, HIV diagnoses, STI screening, STI diagnoses

Figure 1. Study timeline

^a Inclusion dates: 1JAN202X to 31DEC202X of each year

^b Inclusion dates: 21DEC2021 to 30JUN2023, with potential follow-up through 30JUN2024

^c Inclusion dates: 21DEC2021 to 31JUN2024, with potential follow-up through 30JUN2025

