- Coverage by LA PrEP will be determined based on the duration of medication from injection date forward. The number of days of coverage per injection were derived from the CAB LA PrEP USPI label.¹⁴
 - 1st injection: coverage = 37 days (30 days of coverage + 7-day injection window)
 - Subsequent injections: coverage = 67 days (60 days of coverage + 7-day injection window)
 - Each calendar day will only be counted once, even if there is an overlap between coverage from the prior injection and date of the next injection.

$$\% \text{ coverage} = \frac{\sum \min(\text{coverage, days between injections})}{\text{Number of FU days}} \times 100\%$$

HIV testing & STI screening

- HIV testing
 - Assessed within 14 days before PrEP start and over the first 12 months after PrEP start
 - Frequency and rate (per 100 person years) of HIV tests over 12-month period
 - Type of HIV tests (RNA [quantitative, qualitative], antigen/antibody, rapid screen)
 - Timing of HIV tests as recommended by PrEP clinical guidelines⁷
 - Oral PrEP: on-schedule testing defined as receiving an HIV test ≤14 days before/at start, and 3 months (76-104 days) after each test
 - LA PrEP: on-schedule testing defined as receiving an HIV test ≤14 days before/at first injection, and ±14 days of each subsequent injection
 - HIV testing practices (type, frequency) by type of healthcare provider (MD or DO, physician associate, nurse practitioner, other/unknown)
 - HIV testing practices (type, frequency) by clinic type (healthcare center, wellness center, other)
- STI screening
 - Assessed within 14 days before PrEP start and over the first 12 months after PrEP start
 - Frequency and rate (per 100 person years) of STI testing events (testing for multiple STIs on the same day will count as 1 testing event)
 - Type of other STI tests
 - Syphilis
 - Gonorrhea
 - Chlamydia
 - Chancroid
 - Lymphogranuloma venereum

- Mycoplasma genitalium
- Hepatitis B virus (HBV)
- Hepatitis C virus (HCV)
- HSV-2
- Trichomoniasis
- HPV and/or genital warts
- Timing of STI tests as recommended by PrEP clinical guidelines⁷
 - Testing 3 months (76-104 days) after last test
 - Testing 6 months (168-196 days) after last test
 - Testing 12 months (351-379 days) after last test
- STI screening practices (type, frequency) by type of healthcare provider (MD or DO, physician associate, nurse practitioner, other/unknown)
- STI screening practices (type, frequency) by clinic type (healthcare center, wellness center, other)

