HIV test within 14 days before/on day of PrEP type start, n (%)		
Test type		
RNA only, n (%)		
Quantitative RNA test, n (%)		
Qualitative RNA test, n (%)		
Ag/Ab only, n (%)		
Rapid test only, n (%)		
Both RNA and Ag/Ab, n (%)		
Quantitative RNA test, n (%)		
Qualitative RNA test, n (%)		
Both RNA and rapid test, n (%)		
RNA, Ab/Ag and rapid tests, n (%)		
Days from test to PrEP type start, median (IQR)		
Any HIV test within 12 months after PrEP type start, n (%)		
Total number of testing events ^b , N		
Test type		
RNA only, n (%)		
Quantitative RNA test, n (%)		
Qualitative RNA test, n (%)		
Ag/Ab only, n (%)		
Both RNA and Ag/Ab, n (%)		
Quantitative RNA test, n (%)		
Qualitative RNA test, n (%)		
Number of HIV testing events ^b per person, median (IQR)		
Average testing interval per person (#testing events /weeks on PrEP type), median (IQR)		
Testing on schedule (oral: every 3 months (76-104 days); CAB LA: ±14 days of each injection), n (%)		

^a Tests are only counted for the PrEP type used at the time of diagnosis

^b Multiple HIV tests on the same day count as one testing event

Table 15. Frequency and type of HIV tests among oral PrEP users, by healthcare provider type ^a

	MD or DO	Physician Assistant	Nurse Practitioner	Other/unknown
Total number of HIV testing events ^b ordered				
Test type				
RNA only, n (%)				
Quantitative RNA test, n (%)				
Qualitative RNA test, n (%)				
Ag/Ab only, n (%)				
Rapid test only, n (%)				
Both RNA and Ag/Ab, n (%)				
Quantitative RNA test, n (%)				
Qualitative RNA test, n (%)				
Both RNA and rapid test, n (%)				
RNA, Ab/Ag and rapid tests, n (%)				
Testing on schedule (≤14 days before/at start or 3 months (76-104 days) after the last test, as applicable), n (%)				

^a Assessed at the test-level

^b Multiple HIV tests on the same day count as one testing event

Table 16. Frequency and type of HIV tests among CAB LA PrEP users, by healthcare provider type^a

	MD or DO	Physician Associate	Nurse Practitioner	Other/unknown
Total number of HIV testing events ^b ordered				
Test type				
RNA only, n (%)				
Quantitative RNA test, n (%)				
Qualitative RNA test, n (%)				
Ag/Ab only, n (%)				
Rapid test only, n (%)				
Both RNA and Ag/Ab, n (%)				
Quantitative RNA test, n (%)				
Qualitative RNA test, n (%)				
Both RNA and rapid test, n (%)				
RNA, Ab/Ag and rapid tests, n (%)				
Testing on schedule (≤14 days before/at first injection or ±14 days of each subsequent injection, as applicable), n (%)				

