	Oral PrEP N=	CAB LA PrEP N=
HIV testing on schedule (oral: every 3 months (76-104 days); CAB LA: ±14 days of each injection), n (%)		
STI screening every 3 months (76-104 days) ^c , n (%)		
STI screening every 6 months (168-196 days) ^d , n (%)		
STI screening every 12 months (351-379 days) ^e , n (%)		
HIV testing NOT on schedule (oral: every 3 months (76-104 days); CAB LA: ±14 days of each injection), n (%)		
STI screening every 3 months (76-104 days) ^c , n (%)		
STI screening every 6 months (168-196 days) ^d , n (%)		
STI screening every 12 months (351-379 days) ^e , n (%)		

\$(vault:document_date__v)

Protocol for Non-Interventional Studies PASS Studies and Non-PASS Studies (4.0) March 2024

Template Doc ID: TMF-15706807

Parent Doc ID: VQD-SOP-066694

Table 26. STI diagnoses among PrEP users^a

	Oral PrEP N=	CAB LA PrEP N=
STI diagnosis within 14 days before/on day of PrEP type start, n (%)		
Any, n (%)		
Syphilis, n (%)		
Gonorrhea, n (%)		
Chlamydia, n (%)		
Chancroid, n (%)		
Lymphogranuloma venereum, n (%)		
Mycoplasma genitalium, n (%)		
Herpes Simplex-2, n (%)		
Trichomoniasis, n (%)		
Human papilloma virus/genital warts, n (%)		
HBV, n (%)		
HCV, n (%)		
STI diagnosis within 12 months after PrEP type start, n (%)		
Any, n (%)		
Syphilis, n (%)		
Gonorrhea, n (%)		
Chlamydia, n (%)		
Chancroid, n (%)		
Lymphogranuloma venereum, n (%)		
Mycoplasma genitalium, n (%)		
Herpes Simplex-2, n (%)		
Trichomoniasis, n (%)		
Human papilloma virus/genital warts, n (%)		
HBV, n (%)		
HCV, n (%)		

^a Tests are only counted for the PrEP type used at the time of diagnosis

Table 27. Incidence rate of STI diagnoses within 12 months of index among PrEP users^a

	Oral PrEP N=	CAB LA PrEP N=
Total # STI diagnoses within 12 months of index, n		
Person-years of follow-up		
IR per 100 py (95% CI)		

Table 28. Identification of the people who could benefit from PrEP population

	Included N (%)	Excluded N (%)
All individuals in OPERA		
≥1 clinical encounter between 21DEC2021 and 30JUN2023		
≥18 years old at first clinical encounter in study period		
Any indication for PrEP ^a		
No PrEP use between 21DEC2021 and 30JUN2023		

^a Bacterial STI in past 12 months (gonorrhea, syphilis, chlamydia), alcohol use disorder, illicit non-injection drug use, injection drug use. Black woman, transgender woman, men who have sex with men, aged 18-24 years, any history of PrEP use

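### The on-schedule HIV testing rule keeps tests due after oral PrEP is stopped but not after CAB LA is stopped, so Tables 14 and 25 mix discontinuation with testing for oral users only

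*Protocol*

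**What the plan says.** Section 7.3.2 (HIV testing) gives one timing rule per PrEP type. For oral users, each test sets the date of the next one: "Oral PrEP: on-schedule testing defined as receiving an HIV test ≤14 days before/at start, and 3 months (76-104 days) after each test". For injectable users, the date of each injection takes that place: "LA PrEP: on-schedule testing defined as receiving an HIV test ≤14 days before/at first injection, and ±14 days of each subsequent injection".

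Both fall under one assessment period: "Assessed within 14 days before PrEP start and over the first 12 months after PrEP start". For Objectives 2-5, Table 1 in section 7.1 lists the censoring events for Analysis #1 as "Death, loss to follow-up (12 months after last clinical contact), study end (30JUN2024), 12 months after index date". Stopping PrEP is not among them, nor is it in the follow-up rules of 7.3.2.

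In Annex 1, Table 14 puts both types in one row, "Testing on schedule (oral: every 3 months (76-104 days); CAB LA: ±14 days of each injection), n", shown as a count and percentage in an oral and a CAB LA column. Table 25 splits each column by the same rule, and its second stratum is labelled "HIV testing NOT on schedule (oral: every 3 months (76-104 days); CAB LA: ±14 days of each injection), n", again with a percentage.

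Section 5 describes the guideline for oral PrEP in these terms: "it is recommended to repeat HIV testing every 3 months before refilling or reissuing the PrEP prescription".

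**The concern.** The two rules have different anchors. The CAB LA rule follows treatment: where no injection is given, no test is due. The oral rule follows the previous test and runs on for 12 months whether or not oral PrEP continues. Someone with a single injection and a test at that injection is fully on schedule. Someone with a single 30-day oral prescription and the same baseline test still has tests due up to month 12.

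The oral percentage then reflects two things, how well people are tested while on PrEP and how many stay on it. The CAB LA percentage reflects only the first. A reader of Table 14 will take the two columns as the same measure, and the strata of Table 25 will place oral stoppers among those not tested on schedule. The oral rule also drops the tie to the prescription that section 5 describes, while the CAB LA rule keeps its tie to the injection.

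**Working it through.** **Does anything end the oral testing duty at stopping?**

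1. The rule itself has no such condition.
2. Censoring does not. Stopping is not listed. Loss to follow-up is dated 12 months after the last clinical contact, so it cannot shorten the 12-month window for someone whose index start is itself a contact.
3. Study end does not. Figure 1 gives for Analysis #1 "Inclusion dates: 21DEC2021 to 30JUN2023, with potential follow-up through 30JUN2024", so everyone has 12 months of potential follow-up.
4. The shells do not. Table 11, footnote a, runs follow-up for someone who starts on oral PrEP to the first CAB LA injection or 12 months, not to the end of supply. Weeks on PrEP type appears in Table 14 only in the average-interval row.

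**Tests due in 12 months**

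- Oral: 365/104 = 3.5 and 365/76 = 4.8, so 3 to 4 tests fit after baseline. At 90-day spacing there are 4, or 5 with baseline.
- CAB LA, continuing, with injections spaced by the 30- and 60-day coverage in 7.3.2: days 0, 30, 90, 150, 210, 270 and 330, so 7 tests.
- After a single injection: 0 further tests. After a single 30-day oral prescription: still 3 to 4.

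**Illustration.** The protocol states no figure for this outcome, so there is nothing to reproduce. Assumptions, none from the protocol: a share s stops at day 95 in each group; stoppers take no later test; each due test is done independently with probability q, equal in both groups. By day 95 an oral stopper has had 2 tests due (baseline, day 90) and a CAB LA stopper 3 (days 0, 30, 90).

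- Oral as written: (1 - s) × q^5 + s × 0
- Oral, tests due only while on PrEP: (1 - s) × q^5 + s × q^2
- CAB LA: (1 - s) × q^7 + s × q^3

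For q = 0.95 and s = 40%:

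- Oral as written: 0.6 × 0.774 = 0.464
- Oral while on PrEP: 0.464 + 0.4 × 0.9025 = 0.825
- CAB LA: 0.6 × 0.698 + 0.4 × 0.857 = 0.762

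| q | s | Oral as written | Oral while on PrEP | CAB LA |
|---|---|---|---|---|
| 1.00 | 20% | 80% | 100% | 100% |
| 1.00 | 40% | 60% | 100% | 100% |
| 1.00 | 60% | 40% | 100% | 100% |
| 0.95 | 0% | 77.4% | 77.4% | 69.8% |
| 0.95 | 20% | 61.9% | 80.0% | 73.0% |
| 0.95 | 40% | 46.4% | 82.5% | 76.2% |
| 0.95 | 60% | 31.0% | 85.1% | 79.4% |
| 0.90 | 40% | 35.4% | 67.8% | 57.9% |

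If a test is due only when access covers its whole window (to day 104), the day-90 test drops out for a day-95 stopper. The 82.5% then becomes 0.464 + 0.4 × 0.95 = 84.4%.

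The order of the groups depends on s. At q = 0.95, oral as written equals CAB LA when (1 - s) × (0.7738 - 0.6983) = s × 0.8574, that is s = 0.0755/(0.0755 + 0.8574) = 8%. Below that, oral is higher even under the rule as written.

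For scale, the largest confidence interval widths in Table 3 are 0.07 for CAB LA (2 × 1.96 × √(0.25/767) = 0.071) and 0.02 for the oral groups.

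**The case against.** The strongest reply is that no sentence says an oral user owes tests after stopping. The rule sits under a bullet that refers to guideline timing, section 5 describes that guideline for people using oral PrEP, and 7.3.1 defines exposure as time-updated. On that reading tests are due only on PrEP, and the end of the series is a detail for the analysis specification. The reading is possible, but neither the rule nor the shells apply it, and Table 11 points the other way. What remains is a stated rule that yields percentages on different footings, which is more than a missing detail.

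The size is also assumed: s and q do not come from the protocol, and zero testing after stopping is the extreme case. That stands. So does the point that the study is descriptive, with testing rates (Table 13) and events per person (Table 14) shown as well.

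Three stronger readings are tempting and are not supported:

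- *A stopper could not meet the rule even by testing*, because Table 14, footnote a, counts tests only for the type in use. That footnote is garbled (it refers to the time of diagnosis). If a stopper stays classed as oral to month 12, later tests count; if counting ends at stopping, the duty would naturally end too. The claim takes half of each reading.
- *The comparison as a whole favours CAB LA.* Continuing CAB LA users owe 7 tests against 5, which works the other way.
- *Tables 15 and 17 are distorted too.* Both are assessed at test level, so a test never taken does not enter them.

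**Conclusion.** The point holds for the person-level on-schedule row of Table 14 and the strata of Table 25. As written, stopping oral PrEP without further testing is scored as off schedule, and stopping CAB LA after tested injections as on schedule. The stopping effect goes in one direction, against oral. Under perfect testing on PrEP and none afterwards it equals the oral stopping share: 20 to 60 points for assumed shares of 20 to 60%. With q of 0.95 or 0.90 and s = 40% it is about 32 to 36 points for stopping at day 95 (82.5 - 46.4 and 67.8 - 35.4). The protocol gives none of these inputs, so its true size and the net ordering of the groups are unknown. Since no formal comparison is planned, the harm is to how the side-by-side percentages will be read. The definition should be changed before the tables are produced.

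**What to change.** In 7.3.2 and in Tables 14 and 25 only:

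- Define the test-due period in the same way for both types, from the Objective 4 dates. A test is due only while the person has oral access (days-of-supply rule) or CAB LA coverage (37/67-day rule). An oral interval test is due only if access extends through its 76-104 day window.
- Add a row for the share still on the PrEP type at 12 months, so that stopping is visible without being scored as a missed test.
- Keep a calendar-based percentage over the full 12 months, applied to both types, as a secondary row. The calendar interval for CAB LA must then be written down, since 7.3.2 now has only the injection rule.

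Tables 15 and 17 need no change on this account. The change concerns an outcome definition, not testing practice.

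The cost is wording, footnotes and programming on dates already derived. There are three downsides. Early stoppers contribute fewer evaluable intervals. The end of oral access is known only from prescription records, as section 7.9 acknowledges. And because testing may precede a refill, conditioning on continued access can drop people whose missed test led to no refill, which would raise the oral percentage. The secondary calendar row is there to show that effect.

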^a Assessed at the test-level

^b Multiple HIV tests on the same day count as one testing event

Table 17. Frequency and type of HIV tests among oral PrEP users, by healthcare clinic type^a

	Healthcare center	Wellness center	Other
Total number of HIV testing events ^b ordered			
Test type			
RNA only, n (%)			
Quantitative RNA test, n (%)			
Qualitative RNA test, n (%)			
Ag/Ab only, n (%)			
Rapid test only, n (%)			
Both RNA and Ag/Ab, n (%)			
Quantitative RNA test, n (%)			
Qualitative RNA test, n (%)			
Both RNA and rapid test, n (%)			
RNA, Ab/Ag and rapid tests, n (%)			
Testing on schedule (≤14 days before/at first injection or ±14 days of each subsequent injection, as applicable), n (%)			

^a Assessed at the test-level

^b Multiple HIV tests on the same day count as one testing event

Table 18. Frequency and type of HIV tests among CAB LA PrEP users, by healthcare clinic type^a

	Healthcare center	Wellness center	Other
Total number of HIV testing events ^b ordered			
Test type			
RNA only, n (%)			
Quantitative RNA test, n (%)			
Qualitative RNA test, n (%)			
Ag/Ab only, n (%)			
Rapid test only, n (%)			
Both RNA and Ag/Ab, n (%)			
Quantitative RNA test, n (%)			
Qualitative RNA test, n (%)			
Both RNA and rapid test, n (%)			
RNA, Ab/Ag and rapid tests, n (%)			
Testing on schedule (≤14 days before/at first injection or ±14 days of each subsequent injection, as applicable), n (%)			

^a Assessed at the test-level

^b Multiple HIV tests on the same day count as one testing event

Table 19. Incidence rate of STI screening events within 12 months of index among PrEP users^a

	Oral PrEP N=	CAB LA PrEP N=
Total # STI screening events within 12 months of index, n		
Person-years of follow-up		
IR per 100 py (95% CI)		

Table 20. Frequency and type of STI screening among PrEP users^a

	Oral PrEP N=	CAB LA PrEP N=
STI screening within 14 days before/on day of PrEP type start, n (%)		
STI tested, n (%)		
Syphilis		
Gonorrhea		
Chlamydia		
Chancroid		
Lymphogranuloma venereum		
Mycoplasma genitalium		
Herpes Simplex-2		
Trichomoniasis		
Human papilloma virus/genital warts		
HBV		
HCV		
Days from test to PrEP type start, median (IQR)		
Any STI screening within 12 months after PrEP type start, n (%)		
Number of STI screening events ^b , median (IQR)		
Syphilis, n (%)		
Gonorrhea, n (%)		
Chlamydia, n (%)		
Chancroid, n (%)		
Lymphogranuloma venereum, n (%)		
Mycoplasma genitalium, n (%)		
Herpes Simplex-2, n (%)		
Trichomoniasis, n (%)		

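### Two-sided testing windows score more frequent testing as off schedule, unevenly between oral and CAB LA users, and 12-month follow-up truncates the 12-month STI window

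*Protocol*

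**What the plan says.** Protocol section 7.3.2 sets the timing rules for Objective 5.

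- **HIV, oral users:** a test at or within 14 days before start, "and 3 months (76-104 days) after each test". Annex Table 15 states the interval as running from the last test instead.
- **HIV, CAB LA users:** a test at or within 14 days before the first injection, "and ±14 days of each subsequent injection".
- **STI, both groups:** "Testing 3 months (76-104 days) after last test", "Testing 6 months (168-196 days) after last test" and "Testing 12 months (351-379 days) after last test".
- **Period:** tests are assessed from 14 days before PrEP start through the first 12 months. Table 1 of the protocol censors follow-up no later than 12 months after index.
- **Injection spacing:** the coverage rule gives 30 days plus 7 after the first injection, then "Subsequent injections: coverage = 67 days (60 days of coverage + 7-day injection window". Section 5 places CAB LA HIV testing every 2 months, at the injection.

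Annex Tables 14, 20 and 25 report the results by oral versus CAB LA. Table 25 splits people into HIV testing on schedule and not on schedule, then crosses each half with the STI windows.

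Two shells matter as well. "Table 17. Frequency and type of HIV tests among oral PrEP users, by healthcare clinic type" carries the injection-based definition. Table 14 has the row "Average testing interval per person (#testing events /weeks on PrEP type), median (IQR", and Tables 20, 33 and 38 have the same construction.

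**The concern.** A guideline interval is normally read as a maximum: test at least this often. A window with a lower bound treats an early test as a failure just like a late one. Nothing in section 7.3.2 or the Annex credits earlier or more frequent testing.

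Timing relative to the guideline is a named output of Objective 5. Under these definitions some of the apparent poor timing would come from the scoring rule, and it would fall on the most closely tested people. It would also fall unevenly: the lower bound affects oral HIV testing and all STI testing, but not CAB LA HIV testing.

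**Working it through.** **Inputs.** All day counts come from section 7.3.2. I take 12 months as 365 days.

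**1. The plan's windows.** 90 ± 14 = 76-104; 182 ± 14 = 168-196; 365 ± 14 = 351-379. All three reproduce.

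**2. Oral HIV testing.** Take a test every 60 days. From any test, later tests come at 60, 120, 180 days and so on.
- Counting from the last test, every gap is 60, which is below 76.
- If any later test after each test may count, 60 is too early and 120 exceeds 104.

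The person fails on both readings. The wording matters for other patterns. Testing every 45 days fails from the last test (45 < 76) but passes under the looser reading (2 × 45 = 90).

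**3. STI windows.** Gaps below 76 days, of 105-167 days and of 197-350 days meet no window. Screening every 120 days therefore fails even the 6-month row.

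**4. CAB LA STI screening at injection visits.** I assume that screening happens at injections and that injections follow the stated 60 days plus 7.

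| Screen at | Gap (days) | In 76-104? |
|---|---|---|
| every maintenance injection | 60-67 | no |
| every second maintenance injection | 2 × 60 to 2 × 67 = 120-134 | no |
| every third maintenance injection | 180-201 | no (overlaps the 6-month window) |
| injection 1, then 3, none at 2 | 30 + 60 = 90, up to 37 + 67 = 104 | yes |

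The protocol gives no allowance for early injections. If 7 days early is assumed as well, the first two rows become 53-67 and 106-134, with the same answer.

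Nominal injections on days 0, 30, 90, 150, 210, 270 and 330 give gaps of 30, 60, 60, 60, 60, 60. Screening at each one meets a window in 0 of 6 gaps. All 6 gaps are at or below 104 days.

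**5. The 12-month STI window.** For a last test on day d the window runs from d + 351 to d + 379. With follow-up ending on day 365, the visible days for d from -14 to 14 are 365 - (d + 351) + 1 = 15 - d.

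| d | -14 | -7 | 0 | 7 | 14 | 15 or later |
|---|---|---|---|---|---|---|
| visible of 29 | 29 | 22 | 15 | 8 | 1 | 0 |

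**6. Table shells.** Table 17 covers oral users but asks for tests around injections, against section 7.3.2 and Table 15. In the average-interval row, 4 tests in 52 weeks give 4/52 = 0.08 tests per week, whereas the interval is 52/4 = 13 weeks. Tables 33 and 38 divide by weeks on a PrEP type in a population not on PrEP.

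**The case against.** The study is descriptive. Frequent testing stays visible in test counts per person, in rates per 100 person-years (Tables 13 and 19) and in the any-test proportions. That stands, and it confines the problem to the timing rows and Table 25.

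The STI rows can be read as descriptive interval categories. The Table 20 footnotes tie them to different groups and infections, so a 3-monthly tester missing the 6- and 12-month rows is not in itself an error. That also stands, but it does not help someone whose frequent screening meets no row at all, or an oral user placed under not on schedule in Table 25.

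A reader might infer that CAB LA users can never meet the 3-month STI window. The documents do not support this. The gap from injection 1 to 3, a late injection or a screen outside an injection visit can all fall inside it, and section 7.3.2 does not tie STI screening to injections. A reader might also infer that anyone tested every 45 days scores zero, but that needs the Table 15 wording. Nor is the 12-month window simply out of reach: a day-0 test leaves 15 of 29 days visible, just over half.

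The Table 17 and average-interval faults are editorial in origin. The oral rule is stated correctly elsewhere, and the interval row prints its own formula. Followed as written, though, they still give wrong or mislabelled rows.

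**Conclusion.** The concern holds for the timing rows. The oral HIV rule and the STI windows score more frequent testing as off schedule. Regular 60-day oral HIV testing fails under either wording. STI screening at every on-time maintenance injection, or at every second one, misses the 3-month window. Since the CAB LA HIV rule ignores extra tests, the oral and CAB LA on-schedule figures in Tables 14 and 25 do not measure the same thing. The 12-month STI row is truncated, and cannot be met from a last test on day 15 or later.

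How many people this affects cannot be computed, because the protocol gives no distribution of testing gaps. The CAB LA result assumes on-time injections with screening only at those visits.

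**What to change.** 1. Use one wording, counting from the last test, in section 7.3.2 and all tables.
2. Score at person level that no gap between consecutive tests exceeds the plan's own upper limit (104, 196 or 379 days), and label the rows as at least every 3, 6 or 12 months. The existing exclusive windows can stay as a descriptive distribution.
3. In the test-level tables, do not let a repeat test taken shortly after another count as a further met interval. Otherwise an upper limit alone would inflate these rows.
4. Count only gaps whose upper limit falls within observed follow-up. In the nominal CAB LA year above, the gap starting on day 270 drops out (270 + 104 = 374 > 365), leaving 5 of 5 met.
5. For the 12-month STI row, either use follow-up beyond 12 months where it exists or report the row as truncated. Extension departs from the 12-month period of Objective 5. It also adds nothing for people indexed at the end of inclusion, since 30JUN2023 to study end on 30JUN2024 is only 12 months.
6. Put the oral rule in Table 17.
7. Define average interval as weeks observed divided by testing events, with weeks of follow-up in Tables 33 and 38.

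The cost is wording and programming; no new data are needed. The downside is that the rows become cumulative rather than exclusive.
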